## 11. Primary Endpoint

### 11.1. Analysis set

Any interim analysis is based on the ITT analysis set.

All analyses for the final statistical analysis report are based on the ITT analysis set and the per-protocol analysis set. Thereby, subgroup analyses are performed for the ITT analysis set only.

### 11.2. Variables

#### CIP Chapter 8.3.1 Primary Endpoint

*The primary endpoint is the time from randomization (definition see section 8.2.1) to the first MACE during the clinical investigation. Patients without MACE are censored, i.e. the time from randomization until the earliest date of drop-out, study termination, or date of freezing the Clinical Data Management System database (in case of interim analyses) is considered. Patients who reach the primary endpoint will continue to be followed up until the formal termination of the study is announced (see section 8.1).*

*A major adverse cardiac event (MACE) comprises the following events:*

- *Cardiovascular death*
- *Worsening of the patient status due to heart failure, requiring acute unscheduled hospitalization or urgent visit*

*or acute unscheduled hospitalization due to adverse events (AE) of the following list:*

- *Arrhythmia*
- *Acute coronary syndrome*
- *Stroke*
- *Major bleeding*
- *Systemic embolism*

Variables for the ITT analysis set

Data file: Identifier patient_display_id_full	Notes	Variable name	Variable label	Variable level	Nominal values
data_SAR	descr.	any_1pep_ITT_SAR 	Any prim EP occurred at or after effective randomization ITT	nominal	Yes / No
data_SAR	No report	date_1pep_ITT_SAR 	Date of 1st prim EP at or after effective randomization ITT	date	n.a.
data_SAR	descr.	days_effrand_to_1pep_ITT_SAR 	Days from effective randomization to first prim EP or censoring ITT	scale	n.a.

Variables for the per-protocol analysis set

Data file: Identifier patient_display_id_full	Notes	Variable name	Variable label	Variable level	Nominal values
data_SAR	descr.	any_1pep_PP_SAR 	Any prim EP occurred at or after effective randomization PP	nominal	Yes / No
data_SAR	No report	date_1pep_PP_SAR 	Date of 1st prim EP at or after effective randomization PP	date	n.a.
data_SAR	descr.	days_effrand_to_1pep_PP_SAR 	Days from effective randomization to first prim EP or censoring PP	scale	n.a.

### 11.3. Treatment of Missing and Spurious Data

Spurious data, which were not clarified by the query process before CDMS closure, are indicated. If appropriate, descriptive and inferential analyses are performed both with /without such data.

### 11.4. Exclusion of Particular Information

No data from the previous defined analysis set are excluded from the analysis except those defined in chapter 5.5, if applicable.

### 11.5. Descriptive Analyses

If applicable, mean and median survival times are presented by using the Kaplan-Meier estimates. Kaplan-Meier survival figures are presented for illustration.

Other descriptive data will be presented via tables as specified in chapter 5.1.

### 11.6. Hypotheses & Statistical Tests

#### CIP Chapter 7.2 Primary hypotheses

*For assessing the primary endpoints, Kaplan-Meier curves will be constructed for the time to first MACE for both study groups according to the intention-to-treat principle. The hazard ratio is defined as the rate of the BioMonitor group divided by the rate of the control group.*

*The following set of hypotheses (null hypothesis  $H_0$  and alternative hypothesis  $H_A$ ) will be tested. More detailed information about the endpoints is provided in section 8.3:*

- *$H_0$ : Null hypothesis:  $H_0 : HR \geq 1$  which means that monitoring patients of the BioMonitor group will not lead to a longer time-to-first-event of MACE compared to the control group.*
- *$H_A$ : Alternative hypothesis:  $H_A : HR < 1$  which means that monitoring patients of the BioMonitor group will lead to a longer time-to-first-event of MACE compared to the control group.*

*It is expected that there is a  $HR < 1$  in favour of the BioMonitor group. A rejection of the null hypothesis indicates that the BioMonitor group has a statistically significant longer time to first MACE event compared to the control group.*

The confirmatory analysis of the primary hypothesis is performed according to the methods defined in chapter 0. based on the first primary endpoint after the effective randomization date or censoring at the termination date in the ITT analysis set.

The test of the primary hypothesis is repeated according to the methods defined in chapter 0. based on the first endpoint after the effective randomization date for the PP analysis or censoring at the final date for the final PP analyses in the PP analysis set.

In case the primary alternative hypothesis can be accepted, hazard ratios for the BioMonitor versus control group including 95% CI are additionally calculated based on the Cox regression model for the following conditions:

- ITT analysis set, uncorrected adjudication, stratification amikind\_multi= STEMI/NSTEMI
- ITT analysis set, corrected adjudication, stratification amikind\_multi= STEMI/NSTEMI
- ITT analysis set, corrected adjudication, without stratification
- PP analysis set, corrected adjudication, stratification amikind\_multi= STEMI/NSTEMI
- PP analysis set, corrected adjudication, without stratification

The assumption of proportional hazards is checked graphically by log-minus-log survival versus log-time plots.

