### **8.2.3 Other**

Several methods to reduce bias are implemented in this study, including, but not limited to:

- Patient selection according to pre-defined inclusion and exclusion criteria.
- It is the intention of the study design that all patients will be followed-up and treated in accordance with clinical routine/guidelines. Nevertheless, to gather endpoint information all patients will be contacted via telephone on a 6 monthly basis (see section 9.6).
- In case of Home Monitoring findings, patients in the BioMonitor group may have more contacts to the study site, and thus a potentially more complete reporting of endpoints. Nevertheless, the frequency of telephone follow-up calls in both cohorts should remain equal and independent of Home Monitoring findings. Thus, the contract research organization (CRO) in charge of performing the telephone follow-up (see

section 9.6) will remain blinded to information received from other contacts. As a quantitative measure for over-reporting, a separate analysis will be conducted involving only primary endpoints reported by patients during the telephone follow-up calls.

- Standardized procedures/processes for (see section 9):
  - Standardized telephone procedures outlined in a separate telephone manual
  - Standardized methods for data collection, including the documentation of potential confounding factors, such as patient demographics, medical history and procedural parameters
  - Standardized procedures for BioMonitor implantation in accordance with the technical manual
- Formation of a Publication Steering Committee (see section 21).
- Formation of an Endpoint and Adverse Event Committee (EAEC) that will assess all cardiovascular SAEs and all cases of patient death in a blinded and standardized manner regarding the primary endpoint (see section 9.8.1).
- A CEMB will be formed to ensure a standardized interpretation of the Home Monitoring findings and consequent forwarding to the study sites (see section 9.8.5).

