In addition to event triggered in-hospital visits, the patient may have been sent in by a primary or secondary care provider or the patient appears at the site on his own decision. For these cases, the 'General notification form' captures the reason for the visit as well as the types of examinations and therapies performed. If during in-hospital visits, the investigator is notified about adverse events, the information is entered into an AE CRF. To avoid a bias in favour of the control group, which might be introduced as a result of a more complete AE reporting in the BioMonitor group due to possible more frequent contacts, AEs recorded by the investigator during such visits will not be visible to the CRO that performs the regular patient interviews (see section 9.8.6). Thus, it will be possible to estimate a possible underreporting of primary endpoints by looking separately at the information received during the telephone contacts.

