#### **11.1.4 Statistical methods**

Descriptive analyses: The data are presented using descriptive statistical methods. For metric data sets, the mean values, standard deviation, median, maximum and minimum are stated, if appropriate. Ordinal data are described by the median and interquartile range. For nominal data, absolute numbers and relative frequencies are determined.

Inferential analysis of the primary hypothesis: A one-sided log rank test is performed in the context of a confirmatory analysis of the primary hypothesis at the interim and the final analysis.

Explorative multivariable analyses are performed (after the termination of the study, i.e. not after interim analysis) based on the Cox regression model.

Inferential analysis: For the inferential analysis of metric, normal-distributed data, a t-test for interindividual of independent groups or a paired t-test for the intraindividual comparison of paired data is performed. In case the normality assumption of the data is either a priori not justified as specified in the SAP or overtly violated (i.e. by a significant Kolmogorov-Smirnov-Lilliefors or Shapiro-Wilk test result) a non-parametric Wilcoxon-Mann-Whitney rank-sum test or a Wilcoxon-signed-rank test is performed, respectively. For the analysis of relative frequencies, Fisher's exact test is used.

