## **11.2 Sample size**

The original planning assumed that 372 primary events would be required to accept the primary alternative hypothesis with 80% statistical power given an assumed hazard ratio in the population of 0.7452, and the study was to be terminated after this number of endpoints had been collected.

Instead, it was decided to enter the termination phase without any avoidable further delay. Therefore, the intended number of endpoints may not be reached.

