## 5.8. Phase2: Interim analyses (NOTE: Not relevant for the final analysis)

### CIP chapter 8.1 General considerations

In the second phase enrollment will continue in the same way, but in more investigational sites than the first phase, and without interception until up to 2900 patients entered the study.

...

The first and second interim analysis will be performed after 124 and 248 primary endpoints, respectively. Within the interim analyses the primary hypothesis will be tested based on the ITT analysis set. Additionally, the stratified randomization procedure will be checked whether there are severe deviations between the BioMonitor and the control group which indicate a failure of the randomization procedure.

No Clinical Investigation Report will be generated. Any person involved in this analysis is obliged to keep all information confidential. The Statistical Analysis Report will be delivered to the DSMB only. The DSMB will inform the steering committee and the sponsor whether to continue the study without any amendments, continue the study with an amendment (e.g. change of the sample size based on the adaptive design), or stop the study for proven superiority according to the O'Brien-Fleming design. The DSMB is also responsible to give recommendations for stopping the study for safety reasons or for futility, if applicable.

No other analyses will be conducted for the Statistical Analysis Report which is submitted to the DSMB. Only in case the DSMB recommends the discontinuation of the study, and the Sponsor decides to follow this recommendation, the further procedures will be identical to those specified for the final analysis.

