## 10. Pre-processing EAEC data for the primary and secondary endpoints

Each event from the EAEC-adjudication data file is identified by a parent\_record\_id variable. There are at least three data lines per event containing the adjudication of the three board members. In case of deviating decisions of the board members for a specific variable, a 2-of-3 decision is used for further analyses. However, a final adjudication of the chair, which is identified by the variable eac\_complete\_chair = Yes, overrules the evaluations of the other EAEC Members. According to EAEC working procedure, there are at least 2 identical adjudications or a chair decision for each event.

In its initial adjudication, the EAEC classifies the uncorrected cause of the event with all available information including BioMonitor data. Next, for any possible endpoint, the most probably adjudication result without BioMonitor information is documented. The analyses of the endpoints will be based on this variables type\_of\_event\_ae2 and death\_prim\_cause2, which are in better accordance with the objective of the study. However, for the primary endpoint a safety analysis is also performed for the uncorrected variables type\_of\_event\_ae and death\_prim\_cause.

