### 12.6. Hypotheses & Statistical Tests

#### CIP Chapter 7.3 Secondary hypotheses

*The objective to show that arrhythmias requiring guideline-recommended therapy will be detected earlier in the BioMonitor group will be formally tested similarly to the primary hypothesis. The HR is defined as the rate of the BioMonitor group divided by the rate of the control group.*

*H0: Null hypothesis:  $H_0 : HR \leq 1$  which means that monitoring patients of the BioMonitor group will not lead to a shorter time to first arrhythmia that requires guideline-recommended therapy, in the BioMonitor group compared to the control group.*

*HA: Alternative hypothesis:  $H_A : HR > 1$  which means that monitoring patients of the BioMonitor group will lead to a shorter time to first arrhythmia that requires guideline-recommended therapy compared to the control group.*

The hazard ratio for the BioMonitor versus control group including 95%CI is calculated with the Cox regression model. In case of doubt about the validity of the Cox model, the assumption of proportional hazards is checked graphically by log-minus-log survival versus log-time plots.

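### SAP 11.6 plans the primary-endpoint hazard ratio and 95% CI only if the primary test succeeds, so a non-significant trial has no pre-specified effect estimate for first MACE

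*SAP*

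**What the plan says.** The confirmatory method is a significance test. Protocol 11.1.4: "A one-sided log rank test is performed in the context of a confirmatory analysis of the primary hypothesis". SAP 5.2 stratifies the final test by STEMI/NSTEMI, and SAP 11.6 runs it on the ITT set and repeats it on the per-protocol set.

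Estimation comes next in SAP 11.6, under a condition: "In case the primary alternative hypothesis can be accepted, hazard ratios for the BioMonitor versus control group including 95% CI are additionally calculated". Five Cox models follow: ITT uncorrected stratified, ITT corrected stratified, ITT corrected unstratified, per-protocol corrected stratified, and per-protocol corrected unstratified.

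The secondary arrhythmia-detection endpoint has no such condition. SAP 12.6: "The hazard ratio for the BioMonitor versus control group including 95%CI is calculated with the Cox regression model". The same rule stands in SAP 13 to 21 and 23, which makes 11 time-to-event endpoints.

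Three other statements bear on the point:
- SAP 10, on adjudication that uses BioMonitor information: "for the primary endpoint a safety analysis is also performed for the uncorrected variables". No condition is attached and the form of the analysis is not named.
- Protocol 11.2, on the decision to enter the termination phase: "Therefore, the intended number of endpoints may not be reached".
- Protocol 8.2.3, on unequal reporting between the arms: "As a quantitative measure for over-reporting, a separate analysis will be conducted involving only primary endpoints reported by patients during the telephone follow-up calls". Protocol 9.5 relies on the same idea: "it will be possible to estimate a possible underreporting of primary endpoints by looking separately at the information received during the telephone contacts".

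**The concern.** A log-rank test returns a p-value and no effect size. If it is not significant, the reader needs the hazard ratio and its interval to tell an inconclusive trial from one that argues against the planned effect. Under SAP 11.6 that is the case in which neither is planned. The risk is greater here because the trial may stop short of its event target.

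There are two further consequences. First, estimating only after significance selects the favourable results, so the hazard ratio overstates the effect on average when it is reported. Second, SAP 1.4 records that everyone responsible for SAP 3.0 was unblinded. A hazard ratio added after a null result would be post hoc, chosen among five models with treatment data known. This implies no motive; pre-specification removes the question.

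The plan is also uneven. Protocol 8.3.3 concedes that the study is not powered for the individual MACE components, yet their hazard ratios are guaranteed and that of the composite is not.

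**Working it through.** **1. Is there an unconditional estimate elsewhere?**
- SAP 11.5: Kaplan-Meier mean and median times, figures and descriptive tables. No between-group estimate with a CI.
- Protocol 7.2: defines the hazard ratio and the hypotheses, but does not commit to estimating it.
- Protocol 11.1.4 and SAP 5.2: exploratory multivariable Cox models without a named endpoint, covariates or CI.
- SAP 10: an uncorrected-adjudication analysis of unstated form.

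None of these specifies a hazard ratio or CI for first MACE after a null result.

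**2. Inputs.** Design hazard ratio 0.7452, 372 events and 80% power (Protocol 11.2, 11.3); global one-sided alpha 0.025 (11.3); final one-sided level 0.02476 (11.1.1); 1:1 allocation (8.1). The final event count is not stated. The assumed range takes its lower points from SAP 5.8, "The first and second interim analysis will be performed after 124 and 248 primary endpoints", and its upper point from the original target. The values 200 and 300 are added between them.

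**3. The plan's own figure.** Schoenfeld: 4 × (1.960 + 0.842)² / (ln 0.7452)² = 363 events. Freedman gives 369. With three-stage O'Brien-Fleming inflation (factor 1.0174) these become 369 and 375. The stated 372 is reproduced.

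**4. Chance that the condition fails at the design effect.** With SE(log HR) = 2/√D and z = 1.9641 for 0.02476:

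P(no HR) = 1 − Φ(|ln 0.7452| × √D / 2 − 1.9641)

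The largest observed hazard ratio that still triggers the calculation is exp(−1.9641 × 2/√D).

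| Events D | P(no HR) | Largest observed HR that is still estimated |
|---|---|---|
| 372 | 0.192 | 0.816 |
| 300 | 0.280 | 0.797 |
| 248 | 0.363 | 0.779 |
| 200 | 0.454 | 0.757 |
| 124 | 0.628 | 0.703 |

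The probability is 50% at D = (2 × 1.9641 / |ln 0.7452|)² ≈ 178 and is higher below that. If the true hazard ratio is 1, it is about 97.5% at any D (1 − 0.02476).

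**5. What is lost after a null result.** At an assumed 200 events, SE = 2/√200 = 0.1414 and the 95% CI factor is exp(1.96 × 0.1414) = 1.319.
- Observed 0.80: CI 0.61 to 1.06, one-sided p = 0.057. The interval contains 0.7452.
- Observed 1.00: CI 0.76 to 1.32, one-sided p = 0.50. The interval excludes 0.7452.

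Both are non-significant and they mean different things. SAP 11.6 calls for neither estimate.

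**6. Bias from estimating only after significance.** With a true hazard ratio of 0.7452, the geometric mean of the reported value, given significance, is about 0.72 at 372 events and 0.62 at 124.

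**The case against.** - **The probabilities are one minus power at the design effect.** This is correct. They say nothing new about power. They say how often the rule suppresses the estimate.
- **124 events is a boundary.** This is fair. It is the planned first-interim count. SAP 1.4 dates that interim to March 2020, and follow-up was targeted to about October 2021, so the final count probably exceeds 124. The 63% is the end of a range and not a forecast.
- **The contrast at 200 events does not hold everywhere.** This is also fair. An observed hazard ratio of 1.00 excludes 0.7452 only above about 178 events; at 124 the interval is about 0.70 to 1.42. With fewer events, the width of the interval is itself what the reader needs to see.
- **The consequences are limited.** The models are already written down, nothing forbids running them after a null result, and an approximate hazard ratio can be recovered from the log-rank statistic and the event count. This limits the harm but does not close the gap: SAP 1.1 makes mandatory only what the SAP defines, and after a null result the primary hazard ratio is not defined.
- **SAP 10 and 11.6 need not conflict.** An unconditional log-rank test on uncorrected data would satisfy SAP 10. It is therefore an ambiguity to settle and not a contradiction.
- **The telephone-only analysis is a separate matter.** This is true; it is recorded here as a related omission. The variable tables in SAP 10 and 11 list no variable for it, but the derivation footnotes to those tables could not be read for this check.

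**Conclusion.** The concern holds and should be fixed. As written, the plan guarantees a hazard ratio and CI for 11 secondary endpoints and withholds them for the primary endpoint whenever the primary test fails. At the design effect that happens with probability 19% at the full 372 events, rising as events fall to 45% at 200 and 63% at 124. These figures assume proportional hazards, SE(log HR) = 2/√D, a true hazard ratio of 0.7452 and an event range that the documents do not supply. The reading of SAP 11.6 depends on none of them. This is a defect of estimation and reporting; type I error, sample size, the confirmatory test and the analysis set are unchanged.

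**What to change.** 1. In SAP 11.6, delete the opening clause that makes the Cox models depend on the primary result. State that the ITT, corrected-adjudication, STEMI/NSTEMI-stratified hazard ratio with 95% CI is always reported as the primary estimate, and that the other four listed models are sensitivity analyses.
2. In SAP 10, state that the uncorrected-adjudication analysis is the one listed in 11.6 and is done whatever the primary result.
3. Separately, carry the telephone-only analysis of Protocol 8.2.3 into SAP 10 and 11. It should cover every primary endpoint that patients report in the calls, whether or not the site already knew of it. That reading fits Protocol 8.2.3 and 9.5, which keep the calling CRO unaware of information from other contacts.

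Items 1 and 2 cost one deleted clause, one or two added sentences in 11.6, a clarification in SAP 10, and model runs on existing data. Item 3 needs one derived variable for telephone-reported endpoints.

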## 12. Sec. Endpoint: Time to 1st arrhythmia detection

### 12.1. Analysis set

This endpoint is analyzed exclusively for the final statistical analysis report based on the ITT analysis set.

### 12.2. Variables

#### CIP Chapter 8.3.2 Secondary endpoint: Time to first arrhythmia detection

*This secondary endpoint comprises the time from randomization to the detection of an arrhythmia that requires guideline-recommended therapy. Patients without arrhythmia detection are censored, i.e. the time from randomization until the ~~earliest date of drop-out, study termination, or date of freezing the Clinical Data Management System database (in case of interim analyses)~~ is considered.*

To be more precise, secondary endpoints will not be analyzed during interim analyzes and the earliest date of drop-out is just documented as termination date date\_term at the termination CRF.

Data file:Identifier record_id	Notes	Variable name	Variable label	Variable level	Nominal values
advers_events	No report	arr_date	When was the earliest documentation of the arrhythmia?	date	n.a.
adverse_events	No report	arr_yn	Was an arrhythmia documented in the context of this event?	nominal	Yes / No
adverse_events	No report	arrchange_yn	Does the arrhythmia require guideline-recommended change of therapy?	nominal	Yes / No
data_ae_SAR	No report	arrdetect_SAR 	Arrhythmia detection with guideline-recommended change of therapy	nominal	Yes / No
data_ae_SAR	No report	date_arrdetect_SAR 	Date of a arrhythmia detection with guideline-recommended change of therapy	date	n.a.

Data file: Identifier patient_ display_id_full	Notes	Variable name	Variable label	Variable level	Nominal values
data_SAR	descr.	any_arrdetect_ITT_SAR 	Any arrhythmia with guideline-recommended change of therapy after effective randomization ITT	nominal	Yes / No
data_SAR	No report	date_1arrdetect_ITT_SAR 	Date of 1st arrhythmia with guideline-recommended change of therapy after effective randomization ITT	date	n.a.
data_SAR	descr.	days_effrand_to_1arrdetect_ITT_SAR 	Days from effective randomization to 1st arrhythmia detection with guideline recommended therapy or termination ITT	scale	n.a.

